## **7. ADVERSE EVENTS: LIST AND REPORTING REQUIREMENTS**

### **7.1 Definitions**

#### **7.1.1 Adverse Event (AE)**

An adverse event (AE) is any untoward medical occurrence in a patient or clinical investigation subject administered an investigational product. An AE does not necessarily have a causal relationship with the medicinal product.

All such AEs will be collected regardless of expectedness or assumed relationship to study drug.

The criteria for identifying AEs in this study are:

- Any unfavorable and unintended sign (including an abnormal laboratory finding), symptom, or disease temporally associated with the use of an investigational product, whether or not considered related to the investigational product (Note: Every sign or symptom should not be listed as a separate AE if the applicable disease [diagnosis] is being reported as an AE)
- Any new disease or exacerbation of an existing disease. However, worsening of the primary disease should be captured under efficacy assessments as disease progression rather than as an AE.

- Any deterioration in nonprotocol-required measurements of a laboratory value or other clinical test (eg, ECG or x-ray) that results in symptoms, a change in treatment, or discontinuation of study drug
- Recurrence of an intermittent medical condition (eg, headache) not present pretreatment (Baseline)
- An abnormal laboratory test result should be considered an AE if the identified laboratory abnormality leads to any type of intervention, withdrawal of study drug, or withholding of study drug, whether prescribed in the protocol or not

All AEs, regardless of relationship to study drug or procedure, should be recorded beginning from the time the subject signs the study ICF through the last visit. SAEs will be collected for 28 days after the last dose.

Abnormal laboratory values should not be listed as separate AEs if they are considered to be part of the clinical syndrome that is being reported as an AE. It is the responsibility of the investigator to review all laboratory findings in all subjects and determine if they constitute an AE. Medical and scientific judgment should be exercised in deciding whether an isolated laboratory abnormality should be classified as an AE. Any laboratory abnormality considered to constitute an AE should be reported on the Adverse Event CRF.

Abnormal ECG (QTcF) results, if not otherwise considered part of a clinical symptom that is being reported as an AE, should be considered an AE if the QTcF interval is more than 450 ms and there is an increase of more than 60 ms from baseline. Any ECG abnormality that the investigator considers as an AE should be reported as such.

All AEs must be followed for 28 days after the subject's last dose, or until resolution, whichever comes first. All SAEs must be followed to resolution or, if resolution is unlikely, to stabilization.

Subjects with onset of an AE or deterioration of a preexisting AE will be followed until resolution to baseline, start of a new anticancer treatment, or death.

**Every effort must be made by the investigator to categorize each AE according to its severity and its relationship to the study treatment.**

### **Assessing Severity of Adverse Events**

Adverse events will be graded on a 5-point scale according to Common Terminology Criteria for Adverse Event (CTCAE v4.03). Investigators will report CTCAE grades for all AEs (for both increasing and decreasing severity).

#### **7.1.2 Serious Adverse Event (SAE)**

A serious adverse event (SAE) is any untoward medical occurrence that at any dose:

- Results in death

- Is life-threatening (ie, the subject was at immediate risk of death from the adverse event as it occurred; this does not include an event that, had it occurred in a more severe form or was allowed to continue, might have caused death)
- Requires inpatient hospitalization or prolongation of existing hospitalization
- Results in persistent or significant disability/incapacity
- Is a congenital anomaly/birth defect (in the child of a subject who was exposed to the study drug)

Other important medical events that may not be immediately life-threatening or result in death or hospitalization but, when based on appropriate medical judgment, may jeopardize the subject or may require intervention to prevent one of the outcomes in the definition of SAE listed above should also be considered SAEs. Medical and scientific judgment should be exercised in deciding whether expedited reporting is appropriate in such situations.

In addition to the above, events associated with special situations include pregnancy or exposure to study drug through breastfeeding; AEs associated with study drug overdose, misuse, abuse, or medication error. These events associated with special situations are to be captured using the SAE procedures but are to be considered as SAEs only if they meet one of the above criteria. All AEs associated with special situations are to be reported on the CRF whether or not they meet the criteria for SAEs.

All SAEs must be followed to resolution or, if resolution is unlikely, to stabilization.

#### 7.1.3 Death

Death as such is the outcome of a SAE and should not be used as the SAE term itself. The cause of death should be recorded as the SAE term instead. When available, the autopsy report will be provided to the Sponsor.

Grade 5 should be used for events which lead immediately and directly to death, and grade 4 should be used with outcome death for events which lead to death after a longer time period, and that may also be linked to additional morbidities.

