## **12.2 Data Safety Monitoring**

The DF/HCC Data and Safety Monitoring Committee (DSMC) will review and monitor toxicity and accrual data from this study. The committee is composed of clinical specialists with experience in oncology and who have no direct relationship with the study. Information that raises any questions about participant safety will be addressed with the Overall PI and study team.

The DSMC will review each protocol up to four times a year or more often if required to review toxicity and accrual data. Information to be provided to the committee may include: up-to-date participant accrual; current dose level information; DLT information; all grade 2 or higher unexpected adverse events that have been reported; summary of all deaths occurring with 30 days of intervention for Phase I or II protocols; for gene therapy protocols, summary of all deaths while being treated and during active follow-up; any response information; audit results, and a summary provided by the study team. Other information (e.g. scans, laboratory values) will be provided upon request.

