### **13.5 Analysis of Secondary Endpoints**

There is at least 74% probability of observing one or more rare (8% true probability) events, and 93% probability of observing toxicities that have a true occurrence of at least 15%. With 16 treated patients, the maximum width of a 90% two-sided exact binomial confidence interval for any estimated adverse event proportion will be no wider than  $\pm 22\%$ .

Progression-free survival will also be calculated. Progression-free survival, will be defined as the duration of time from start of treatment to time of progression or death, whichever occurs first and will be estimated using the Kaplan-Meier method. The disease control rate (Complete Response, Partial Response, and Stable Disease) at 24 weeks will also be calculated using the exact binomial distribution and 95% confidence interval.

We will explore the relationship between integrated biomarkers detected by cfDNA exome sequencing, WES, RNAseq expression profiling and response to Eribulin. We will use Fisher's Exact Test to assess the relationship between each biomarker and response to eribulin assuming a best overall objective response of 35%. Biomarkers may be continuous or binary. For example, with this design, assuming tissue is available on 100% of the sample, the probability of concluding eribulin response is related to the exploratory biomarker is 82%; given the unknown true response is 70% and 4% in positive marker versus negative marker patients, respectively, assuming 50% of the population is over-expressed for the biomarker or the biomarker is continuous and split at the median. The operating characteristics of this design are calculated using a two-sided exact test with 10% type I error.

We will explore the relationship between changes in the integrated biomarkers from baseline to cycle 3 due to eribulin treatment using a paired t-test. With 16 patients, we will have 81% power to detect an effect size of 0.67 using a paired t-test with a 0.1 two-sided significance level.

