### **13.6 Reporting and Exclusions**

### 13.6.1 Evaluation of Toxicity

All participants will be evaluable for toxicity from the time of their first treatment. All patients who receive at least one dose of Eribulin will be included in the toxicity analysis. This includes participants who receive study drug and are ultimately deemed ineligible.

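### Section 7.1.3 lets the same fatal adverse event be recorded as grade 4 or grade 5 with no cut-off, so a safety summary by grade could understate fatal events

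*Combined protocol and SAP*

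**What the plan says.** Section 7.1.3 (Death) first makes death an outcome and not an event term: "Death as such is the outcome of a SAE and should not be used as the SAE term itself". It then divides events that lead to death between two grades. On one side, "Grade 5 should be used for events which lead immediately and directly to death". On the other, "grade 4 should be used with outcome death for events which lead to death after a longer time period", and the sentence adds that such events may also be linked to other morbidities. No number of days, and no other test, separates the two.

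Under Assessing Severity of Adverse Events in section 7.1.1, the rule is general: "Adverse events will be graded on a 5-point scale according to Common Terminology Criteria for Adverse Event (CTCAE v4.03"). Investigators are to report grades for rising as well as falling severity. No exception is made for the time to death.

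Section 7.1.2 lists "Results in death" as a criterion for a serious event, with no condition on grade or timing. Section 12.2 says that the monitoring committee may be given a "summary of all deaths occurring with 30 days of intervention for Phase I or II protocols".

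On analysis, section 13.6.1 says "All patients who receive at least one dose of Eribulin will be included in the toxicity analysis". Section 13.5 gives the precision: "With 16 treated patients, the maximum width of a 90% two-sided exact binomial confidence interval for any estimated adverse event proportion" is put at no more than ±22%. Neither section defines a fatal event, specifies a table by grade, or says whether fatal events are identified by grade or by outcome.

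**The concern.** Two investigators can follow 7.1.3 faithfully and give the same fatal toxicity different grades, because the rule turns on an undefined judgement of how promptly and directly death followed. An event that worsens until the patient dies has increased in severity, yet under 7.1.3 it may stop at grade 4.

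The safety profile is a secondary objective (section 1.3). Grade is recorded for every adverse event, and the protocol's own account of the earlier sarcoma study in section 2.2.3 reports toxicity as grade 3 or 4 combined. If this trial's results are tabulated in that style, delayed deaths would sit among non-fatal grade 4 events, and a grade 5 row would leave them out. In so small a trial a single event decides whether the fatal row is empty.

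**Working it through.** **Inputs.** n = 16 treated patients, true event rates of 8% and 15%, and 90% exact intervals, all from section 13.5. The share of fatal adverse events that are delayed, and so graded 4, is called f. The documents do not give it, so it is an assumption, shown over its full range from 0 to 1.

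**Step 1: reproduce the plan's safety figures.** The chance of seeing at least one event is 1 − (1 − p)^16.
- p = 0.08: 1 − 0.92^16 = 73.7% (plan: 74%).
- p = 0.15: 1 − 0.85^16 = 92.6% (plan: 93%).
- The widest 90% Clopper-Pearson interval is at 8/16, from 27.9% to 72.1%, a half-width of 22.1% (plan: ±22%).

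All three agree to rounding, and none depends on the rule in 7.1.3.

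**Step 2: one delayed fatal event in 16 patients.**

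| Count used | Estimate | 90% exact interval | 95% exact interval |
|---|---|---|---|
| By outcome = death | 1/16 = 6.3% | 0.3% to 26.4% | 0.2% to 30.2% |
| By grade 5 only | 0/16 = 0% | 0% to 17.1% | 0% to 20.6% |

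The intervals overlap heavily. What changes is whether a fatal event is reported at all.

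**Step 3: how far a grade 5 count could fall short.** The chance of at least one grade 5 event is 1 − (1 − p(1 − f))^16, and the expected number of grade 5 events is 16p(1 − f). The 8% and 15% are the plan's rates for any toxicity. They are borrowed here as hypothetical fatal-event rates, for scale only.

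| f (assumed) | p = 8%: chance of any grade 5 | Expected grade 5 | p = 15%: chance of any grade 5 | Expected grade 5 |
|---|---|---|---|---|
| 0 | 73.7% | 1.28 | 92.6% | 2.40 |
| 0.25 | 62.8% | 0.96 | 85.2% | 1.80 |
| 0.5 | 48.0% | 0.64 | 71.3% | 1.20 |
| 0.75 | 27.6% | 0.32 | 45.7% | 0.60 |
| 1 | 0% | 0 | 0% | 0 |

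The expected number of fatal events counted by outcome stays at 16 × 0.08 = 1.28, or 16 × 0.15 = 2.40, in every row.

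**The case against.** The strongest reply is that the plan contains no table that this rule would spoil. Section 13.5 speaks of adverse event proportions in general, and 13.6.1 only defines the population. The protocol treats death as an outcome, and the sentence at issue requires that outcome to be recorded alongside grade 4. A fatal-event rate taken from the outcome field is right for any split between the grades. A delayed death would also still appear in any tally of grade 3 and above. All of this stands. A reader might infer that deaths will be hidden, or that the reported fatal rate will be wrong; the documents support neither.

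The rule is also not purely a matter of time. It refers to directness and to other morbidities, so it partly concerns attribution. That is correct, but it supplies no boundary either.

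Finally, a reader might infer that 7.1.3 breaks the CTCAE definition of grade 5. The protocol names the scale without reproducing that definition, so the breach cannot be shown from the documents. What can be shown is that 7.1.1 sets one scale without a timing exception and 7.1.3 adds one.

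These replies do not settle how fatal events will be counted. The committee's summary of deaths is something that may be provided. It covers 30 days from intervention, so it can miss later deaths, the kind most likely to be graded 4.

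**Conclusion.** The point holds as a gap in definition and reporting. Section 7.1.3 makes the grade of a fatal event depend on an undefined judgement, and the statistical section does not say that fatal events are counted by outcome. A summary by grade, if one is made, could understate fatal events and mix them with non-fatal grade 4 events.

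The illustrated size is 0/16 instead of 1/16 for one delayed fatal event. It rests on two assumptions: that such an event occurs, and that fatal events are read from grade 5 alone. The documents give no expected number, and it is probably low. Nothing in the primary analysis is touched, and no sample size, power or type I error changes. This is a minor point that is worth correcting because the correction costs so little.

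**What to change.** Add one sentence to section 13.5 or 13.6.1: adverse events with a fatal outcome are counted and tabulated as fatal by the recorded outcome, whatever the recorded grade or the interval to death. This needs no new data, because 7.1.3 already requires the outcome. It is better than relabelling grade 4 events as grade 5 in the tables, which would make the report disagree with the case report form.

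Alternatively, remove the time-to-death split from 7.1.3 so that it agrees with the single scale in 7.1.1.

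Either change is a small text edit. The only downside is that the reported fatal-event count may be slightly less favourable.

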#### 7.1.4 Life-threatening Event

Any event in which the patient was at risk of death at the time of the event is considered life-threatening; it does not refer to an event which hypothetically might have caused death if it were more severe.

#### 7.1.5 Hospitalization or Prolongation of Hospitalization

Any AE requiring hospitalization (or prolongation of hospitalization) that occurs or worsens during the course of a patient's participation in a clinical trial must be reported as a SAE unless exempted from SAE reporting. Prolongation of hospitalization is defined as any extension of an inpatient hospitalization beyond the stay anticipated/required for the initial admission, as determined by the Investigator or treating physician.

The following hospitalizations are not considered to be SAEs because there is no “adverse event” (ie, there is no untoward medical occurrence) associated with the hospitalization:

- Hospitalizations for respite care
- Planned hospitalizations required by the protocol
- Hospitalization planned before informed consent (where the condition requiring the hospitalization has not changed after study drug administration)
- Hospitalization for administration of study drug or insertion of access for administration of study drug
- Hospitalization for routine maintenance of a device (eg, battery replacement) that was in place before study entry

Other situations that MUST NOT be considered as hospitalizations are the following:

- a. An emergency visit due to an accident where the patient is treated and discharged.
- b. When the patient is held 24 hours for observation and finally is not admitted.
- c. Planned treatments at sites not associated to a hospital and generally considered as minor surgical procedures (i.e., laser eye surgery, arthroscopy, etc.).

#### 7.1.6 Unlisted/Unexpected Adverse Event

An AE, the nature or severity of which is not consistent with the applicable reference safety information.

The Sponsor and the Sponsor designee will use as the reference safety information for the evaluation of listedness/expectedness in the IB and the Summary of Product Characteristics (SmPC) for Eribulin as described in the FDA package insert.

#### 7.1.7 Adverse Reactions

All untoward and unintended responses to an investigational medicinal product related to any dose administered. This definition covers also medication errors and uses outside what is foreseen in the protocol, including overdose, lack of efficacy, misuse and abuse of the product.

Overdose	Accidental or intentional use of the study drug in an amount higher than the protocol-defined dose ( If applicable, define the study-specific criteria for overdose that should be applied when determining whether an overdose occurred. )
Misuse	Intentional and inappropriate use of study drug not in accordance with the protocol ( Use the following definition, if appropriate, for postmarketing studies ) Intentional and inappropriate use of study drug not in accordance with the prescribed or authorized dose, route of administration, or indication(s) or use of prescription-only study drug without a prescription
Abuse	Sporadic or persistent intentional excessive use of study drug accompanied by harmful physical or psychological effects

Medication error      Any unintentional event that causes or leads to inappropriate study drug use or subject harm while the study drug is in the control of site personnel or the subject.

All AEs associated with overdose, misuse, abuse, or medication error should be captured on the Adverse Event CRF and also reported using the procedures detailed in Reporting of Serious Adverse Events (Section 7.2.2) even if the AEs do not meet serious criteria. Abuse is always to be captured as an AE. If the AE associated with an overdose, misuse, abuse, or medication error does not meet serious criteria, it must still be reported using the SAE form and in an expedited manner but should be noted as nonserious on the SAE form and the Adverse Event CRF.

#### 7.1.8 Adverse Events Related to the Study Drug

An AE is considered related to a study drug/IMP if the Investigator's assessment of causal relationship to the IMP(s) is "Y (yes)" (see Section 7.1.10).

The Investigator will assess the causal relationship of the IMP(s) to the SAE.

The Sponsor may also consider related to the study drug(s)/IMP(s) those events for which the Investigator assesses the causal relationship with the IMP(s) as "Uk (unknown)" when it cannot rule out a role of the IMP(s) in the event.

#### 7.1.9 Expedited Reporting

The Sponsor is responsible for the appropriate expedited reporting according to the applicable legislation.

#### 7.1.10 Assessment of Causal Relationship to the Study Drug

### **Assessing Relationship to Study Treatment**

Items to be considered when assessing the relationship of an AE to the study treatment are:

- Temporal relationship of the onset of the event to the initiation of the study treatment
- The course of the event, especially the effect of discontinuation of study treatment or reintroduction of study treatment, as applicable
- Whether the event is known to be associated with the study treatment or with other similar treatments
- The presence of risk factors in the study subject known to increase the occurrence of the event
- The presence of nonstudy, treatment-related factors that are known to be associated with the occurrence of the event

### *Classification of Causality*

The relationship of each AE to the study drug will be recorded on the CRF in response to the following question:

Is there a reasonable possibility that the study drug caused the AE?

Yes (related) A causal relationship between the study drug and the AE is a reasonable possibility.

No (not related) A causal relationship between the study drug and the AE is not a reasonable possibility.

## **7.2 Adverse Events Reporting Procedures**

### **7.2.1 Reporting Adverse Events**

The Sponsor will collect AEs until 28 days after administration of the last dose of study drug(s)/IMP(s), or until resolution, whichever comes first. All AEs suspected to be related to the study drug/IMP must be followed-up after the time of therapy discontinuation until the event or its sequelae resolve or stabilize at an acceptable level to the Investigator and the Sponsor.

All AEs, including misuse, overdose and abuse, must be recorded in English using medical terminology in the source document and the CRF. Whenever possible, the Investigator will record the main diagnosis instead of the signs and symptoms normally included in the diagnoses.

Investigators must assess severity (grade) of the event following the NCI-CTCAE v. 4 and assign a relationship to each study drug(s)/IMP(s); and pursue and obtain information adequate both to determine the outcome and to assess whether it meets the criteria for classification as a SAE requiring immediate notification to the Sponsor and the Sponsor designee. The Investigator must provide any relevant information as requested by the Sponsor or the Sponsor designee in addition to that on the CRF.

Abnormal laboratory tests occurring during the study should only be recorded in the AE section of the CRF if the disorder:

- Is associated with clinically significant symptoms, and/or
- Leads to a change in study dosing or discontinuation from the study, significant additional concomitant drug treatment or other therapy, and/or
- Leads to any of the outcomes included in the definition of a SAE.

Otherwise laboratory results should be reported in the corresponding section of the CRF (e.g. biochemistry, hematology).

All episodes of febrile neutropenia must always be reported within 24 hours following the same procedure for reporting SAEs (see Section 7.2.2), including episodes that occurred in patients without seriousness criteria. For these cases, the seriousness criterion should be reported as a medically significant event.

